- Separated (3)
- Other (please explain): (4)

Were you living with your parents during your senior year of high school?

- Yes (1)
- No (0)

Who were you living with most of the time during your senior year of high school?

- Mother (1)
- Father (2)
- Other (please explain): (3)

Where are you **currently** living?

- With my parent(s) (1)
- In the LMU dorms (2)
- Off campus with roommates (3)
- Off campus alone (4)
- Other (5)

How often do you see or communicate with your **father** in person or online?

- Never (0)
- Less than monthly basis (1)
- Monthly basis (2)
- Weekly basis (3)
- Daily basis (4)

How often do you see or communicate with your **mother** in person or online?

- Never (0)
- Less than monthly basis (1)
- Monthly basis (2)
- Weekly basis (3)
- Daily basis (4)

The next set of questions will ask about your drinking habits. You may not know the exact answer to all of these questions; in those cases, please make your best guess. Please keep in mind that your responses to the questions in this survey are confidential.

How old were you when you had your first drink of alcohol (more than a sip or a taste)?

▼ I have never tried alcohol (0) ... 21 or older (10)

Who gave you your first drink of alcohol (more than just a sip or taste)?

- Parent (1)
- Family member (not a parent) (2)
- Friend (3)
- Stranger (4)
- I have never tried alcohol (0)

Which best describes your alcohol use?

- I have never tried alcohol (0)
- I am an abstainer (I do not drink at all, but have tried before) (1)
- I am a light drinker (2)
- I am a moderate drinker (3)
- I am a heavy drinker (4)
- I am a problem drinker (5)

This section asks you to report on your drinking over the **past 30 days**.

For all questions, **one drink equals**:

Consider a typical week during the past 30 days. How much alcohol, on average (measured in number of drinks), do you drink on each day of a typical week? If your answer is zero, please enter 0.

	Monday (1)	Tuesday (2)	Wednesday (3)	Thursday (4)	Friday (5)	Saturday (6)	Sunday (7)
Number of drinks							

During the **past 30 days**, on average, how many days per week did you drink?

▼ 0 (1) ... 7 (7)

During the **past 30 days**, on average, how many drinks did you have each time you drank?

▼ 0 (0) ... 25+ (25)

During the **past 30 days**, what is the **maximum** number of drinks you drank during any one drinking occasion?

▼ 0 (0) ... 25+ (25)

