Think of the occasion you drank the most in the **past 30 days**. How many **hours** did you spend drinking on that occasion?

During the **past 30 days**, how many times did you have [four/give] or more drinks within a 2 hour period?

▼ 0 occasions (0) ... 7+ occasions (7)

During the **past 30 days**, how many times did you have [eight/ten] or more drinks within a 2 hour period?

▼ 0 occasions (0) ... 7+ occasions (7)

Note: The BYAACQ was used in place of the RAPI to measure alcohol consequences.

Below is a list of things that sometimes happen to people either during or after they have been drinking alcohol. Next to each item below, please indicate whether that item describes something that has happened to you in the **past 30 days**.

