PRS Cover Page for Statistical Analysis Plan

Title: Parent Feedback Intervention Targeting Student Transitions and Alcohol Related Trajectories (+) Efficacy Study (FITSTART+)

Date: April 26, 2021

ClinicalTrials.gov Identifier: NCT04549454

Statistical Analysis Plan

Examines the efficacy of FITSTART+. Main effects of the intervention will be examined with hierarchical generalized linear models (HGLM) using SAS. HGLM permits the simultaneous examination of relationships among variables at different levels, for example variables measured over assessment periods assumed to fluctuate within an individual (e.g., student drinking behavior) with variables considered to have stable characteristics (i.e., parent intervention condition). Using this framework, time will be specified as a Level 1 varying predictor nested within individuals (Level 2). The following model will be used to determine main effects of the intervention conditions compared to control:

$$\text{Level 1: } DV_{ti} = \pi_{0i} + \pi_{1i}(T1)_{ti} + \pi_{2i}(T2)_{ti} + \varepsilon_{ti}$$

$$\text{Level 2: } \pi_{0i} = \beta_{00} + \beta_{01}(Tx)_i + r_{00i}$$

$$\pi_{1i} = \beta_{10} + \beta_{11}(Tx) \quad t \text{ indexes repeated measure} \quad \pi_{2i} = \beta_{20} + \beta_{21}(Tx) \quad i \text{ indexes individuals}$$

Respective model DVs will include total drinks per week from the DDQ, consequence composite score, and number of HED episodes during the past month. T1 and T2 will be dummy coded time variables (T1 = student baseline [coded 0] to 1 month into college follow-up [coded 1], T2 = student baseline [coded 0] to 6 months into college follow-up [coded 1]). Tx will be a categorical predictor comparing the intervention condition [coded 1] to control [coded 0]. With this model, intercept treatment differences will represent treatment differences at baseline (e.g., group differences in student drinking at baseline) and slope differences will represent changes over time (e.g., did students of intervention parents reduce their drinking between baseline and follow-up assessments more than students of control parents?). The intercept includes a random effect, which will model the subject-specific heterogeneity in the outcome and control for correlated data due to individuals. Pairwise comparisons (post hoc Tukey's) were conducted to examine mean differences between conditions at each time point.

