Missing data. Attrition bias will be tested by evaluating whether baseline outcomes differ between student and parent dropouts versus completers. HGLM is optimal in that it allows for unbalanced data, giving heavier weights to participants with more non-missing values. HGLM also assumes that missing values are missing at random as opposed to non-ignorable. The pattern-mixture approach to non-ignorable missing data will be used to assess the sensitivity of findings to the presence of missing data. If the pattern of missingness appears to pose a threat to the validity of the experimental manipulation (i.e., student attrition is related to parent random assignment, or the predictors of attrition are different for students of intervention vs control parents), more powerful missing techniques will be used, such as multiple imputation.

Additional Model Considerations. Student outcomes (drinks per week, HED frequency, and negative consequences) are count variables, which can have skewed distributions when the overall mean is low. Alternative models could also specify a Poisson or Gaussian distribution for the Level 1 errors. We will consider whether the

Level 1 components are more appropriately modeled as Gaussian or Poisson. Further, in spite of randomization at the parent level, we will conduct baseline equivalence tests between the FITSTART+ student participants to establish successful parent randomization effectiveness, including pre-treatment alcohol use, negative consequences, and demographic variables. Any student variables that are associated with treatment assignment, in spite of parent randomization, will be included as covariates.

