Power. *We have more conservatively aimed for sufficient statistical power to detect small effects on our primary student drinking outcomes (i.e., HED frequency, drinks per week, negative consequences).* Very low student attrition (13%) was achieved in the original FITSTART study across 10 months and three assessments. As identical procedures and similar assessments will be used in the current study, we expect to retain over 85% of students. Power analyses were calculated using the Optimal Design program for longitudinal HLM specifying two-study conditions and randomization at the person-level. Power curves with 20% attrition were plotted for sample size per treatment arm at two effect sizes: $d=.20$ (small effect) and $d=.40$ (medium effect). A sample size of 300 per arm was found to yield excellent power for detecting both effect sizes.

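### If the SAP's Poisson option is used, nothing in the model accounts for wave-to-wave variation beyond Poisson, so the Tx-by-time standard errors can be wrong, and too small when that variation is large

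*SAP*

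**What the plan says.** The SAP's model section nests three waves within students and tests the intervention through the Tx-by-time terms (β11 and β21). Its only variance component above Level 1 is on the intercept: "The intercept includes a random effect, which will model the subject-specific heterogeneity in the outcome and control for correlated data due to individuals". The equations for the two time slopes carry no random term.

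Under Additional Model Considerations the SAP calls drinks per week, HED frequency and negative consequences count variables that may be skewed when the mean is low. It then says "Alternative models could also specify a Poisson or Gaussian distribution for the Level 1 errors" and that it will consider whether the "Level 1 components are more appropriately modeled as Gaussian or Poisson". The Power paragraph calls all three outcomes primary.

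Neither document mentions overdispersion, a scale parameter, a negative binomial model, a random slope, an observation-level random effect or robust standard errors. Neither gives a rule for choosing between the two distributions.

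Three features of the Protocol's Measures Appendix also matter. The drinks item is self-averaged: "How much alcohol, on average (measured in number of drinks), do you drink on each day of a typical week". The HED items stop at 7+ occasions. The consequence measure is a checklist ("please indicate whether that item describes something that has happened to you in the" past 30 days), so its score is bounded.

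**The concern.** A Poisson model ties the variance to the mean. The random intercept handles stable differences between students, but not a student whose own rate moves up or down between waves for reasons other than treatment and the common time trend. The efficacy tests are contrasts in change between waves, so that is the variation their standard errors need to reflect. An analyst could follow the SAP to the letter, choose Poisson, report model-based standard errors, and so test three primary outcomes at an error rate that is not the nominal one. A larger sample does not cure this, because the ratio of true to model standard error does not depend on n.

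**Working it through.** The plan has no figure to reproduce here: it reports no outcome means, variances or dispersion.

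**Inputs.** From the SAP Power paragraph: 300 per arm and 20% attrition ("Power curves with 20% attrition were plotted for sample size per treatment arm"), so 300 × 0.8 = 240 per arm. Assumed:
- two-sided 5% tests;
- a baseline mean m0 and a follow-up mean m1;
- a lognormal student effect u with mean 1 and log-SD .7 to 1;
- a wave-specific multiplier on the student's rate with mean 1 and coefficient of variation CV.

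CV is zero if a student departs from the common trend only by Poisson noise.

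**Model standard error.** With complete data, the random-intercept Poisson likelihood splits into a part for student totals and a part for how each total divides across waves. The Tx-by-time estimate is the log ratio of arm-by-wave totals, and its model variance is the sum of 1/total over the four cells:

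model variance = (2/n)(1/m0 + 1/m1)

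**True variance.** The wave multiplier adds CV² × E(u²) per student at each of the two waves, with E(u²) = exp(SD²):

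true variance = (2/n)[1/m0 + 1/m1 + 2·CV²·exp(SD²)]

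Hence (true SE / model SE)² = 1 + x, with x = 2·CV²·exp(SD²)/(1/m0 + 1/m1). The sample size cancels. Two-sided type I error is 2[1 − Φ(1.96/√(1+x))].

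**One case in full.** Take m0 = 3, m1 = 5, SD = .7 and CV = 50%.
- 1/3 + 1/5 = .533 and exp(.49) = 1.632.
- x = 2 × .25 × 1.632/.533 = 1.53, so the SE ratio is √2.53 = 1.59.
- 1.96/1.59 = 1.23, which gives 21.8%.
- With SD = 1, exp(1) = 2.718, x = 2.55, the ratio is 1.88 and the error is 29.8%.

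**Results** (range over SD .7 to 1; CV 22% means CV² = .05):

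| Assumed means | CV 22% | CV 50% |
|---|---|---|
| 3 and 5 | 8.6–11.1% | 21.8–29.8% |
| 1 and 1.5 | 6.1–6.9% | 10.8–14.6% |
| .5 and .75 | 5.6–5.9% | 7.9–9.9% |

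At CV = 0, x = 0 and the error is 5%. The errors are symmetric under the null, so about half of each figure is false benefit, against a nominal 2.5%.

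**Opposite direction.** If a self-averaged typical week carries no counting noise, the squared ratio is x rather than 1 + x. At means 3 and 5, x = 1 when CV² = .533/(2 × 1.632) = .163 (CV 40%) for SD .7, and when CV² = .533/(2 × 2.718) = .098 (CV 31%) for SD 1. Below that the Poisson SE is too large; above it, too small.

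**Simulation with dropout.** Full maximum-likelihood random-intercept Poisson fits were run with 300 per arm and 20% lost by 6 months, missing at random as the SAP assumes ("HGLM also assumes that missing values are missing at random as opposed to non-ignorable"). With model SEs and assumed means 3, 5 and 5, drinks gave 8–9% at CV 22%, 18–25% at CV 50%, and 5–6% with no excess. HED capped at 7 (assumed means 1, 1.5 and 1.5 before the cap) gave 8–10% at CV 50%. The typical-week version without counting noise gave 0–0.5% at CV 22%. The bounded checklist (15 or 24 items assumed) gave 1–4% with no wave-to-wave excess and 15–26% at the largest excess tried (wave SD 1 on the logit scale). Student-clustered sandwich SEs on the same fits gave 3.2–7.6% over all settings, averaging 5.1–5.7% per outcome. The Gaussian option gave 3.2–7.9%.

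**The case against.** The strongest reply is that the harm is conditional. Poisson is only something the alternative models could specify, and the Gaussian form estimates its own residual variance. That stands: the point concerns one of two permitted analyses.

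The larger rates also need means of 3 to 5 and a CV of 50%, neither of which the documents give. The SAP raises the distribution question for counts with a low mean, where the inflation is smaller. That stands too, and is why the low-mean rows are shown. A common shift between July and college is absorbed by the time terms; only unequal changes between students count.

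One might say that the Level 1 error ε supplies the missing variance. It does not: it is written on the outcome scale, and under this option the SAP makes the Level 1 errors themselves Poisson.

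A reader might infer that the analyst would be steered to Poisson anyway, because a likelihood criterion would prefer it. The documents do not support that. The SAP names no criterion, and AIC goes either way. It chose Poisson in every simulated data set at means 3, 5 and 5 with log-SD .7 to 1 and CV 71%, but Gaussian in 6 of 6 at means 6, 10 and 10 with CV 100%. AIC neither reliably selects nor avoids the affected option.

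That a competent analyst would check dispersion anyway is plausible, but the plan does not say so, and the choice would then be made after the outcomes are seen.

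**Conclusion.** The gap is real and worth fixing. If Poisson is used as the SAP stands, the Tx-by-time standard errors leave out wave-to-wave variation within students beyond Poisson. Confidence is high in the missing provision and the mechanism, and low in any rate for this trial. The illustrative two-sided error runs from about 6% (means .5 and .75, CV 22%) to about 30% (means 3 and 5, CV 50%, log-SD 1). It rests on complete data, 240 per arm and the assumed means, student spread and CV.

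A reader might infer that the Poisson standard errors must be too small, or that the trial will produce false claims of benefit. Neither follows. For the typical-week item and the bounded checklist the error can run the other way, about half of any excess rejections would point against the intervention, and nothing arises in this way if the Gaussian form is used.

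**What to change.** Before outcome data are analysed, name one Level 1 distribution for each outcome under Additional Model Considerations. Wherever Poisson is named, keep the random-intercept model and base the Tx-by-time tests and confidence intervals on student-clustered robust (sandwich) standard errors, which correct the SE in either direction. Report the other distribution as a sensitivity analysis. A negative binomial Level 1 or an observation-level random effect is an optional alternative for drinks per week and HED. The negative binomial was checked only lightly here (100–150 complete-data fits per setting, about 5%).

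The cost is a few SAP sentences and a small change to the SAS code; data collection does not change. Intervals move with the data. In the dropout simulations those for drinks widened by a factor of 1.13–1.18 at CV 22% and 1.5–1.7 at CV 50%. The factor for HED was 1.10–1.37 at CV 50–100%. For consequences it was 0.83–1.70, so those intervals can also narrow. With no excess variation the change costs almost nothing: in complete-data runs type I error was 4.8–5.0% with model SEs and 5.1–5.2% with robust SEs.

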12. RANDOMIZATION

Describe criteria for assigning subjects to sub-groups such as "control" and "experimental."

Although the participants among whom outcomes will be assessed are students, parents of these students will be the ones randomized to the treatment or control version of the app. A verification form on the informational FITSTART+ landing page, will serve two important purposes: (1) it will match parents to their students in the dataset; and (2) randomize parents to the treatment or control version of the app. The randomizer will be set up in Qualtrics to balance assignment to an app condition by students' birth sex. At the end of the verification form, parents will receive a web URL linking to the sign-up page for the application to which they were randomized. The treatment condition will receive the FITSTART+ intervention while the control group will receive a similar program which covers all non-alcohol related resources included in the intervention version of FITSTART+ (e.g., general parenting information, university-specific resources).

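### Covariates enter the primary models only if a baseline test links them to arm, so chance imbalance rather than relation to drinking decides the adjustment

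*SAP*

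**What the plan says.** The SAP introduces its model with "The following model will be used to determine main effects of the intervention conditions compared to control". The equations contain the two time indicators, treatment, their interactions and a random intercept, and no covariates. The outcome's own baseline is the first repeated measure: "intercept treatment differences will represent treatment differences at baseline", and the intervention effect is read from the slope differences. The same section also plans Tukey comparisons of the arm means at each time point.

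The only route for a covariate is under Additional Model Considerations. There the SAP says "we will conduct baseline equivalence tests between the FITSTART+ student participants to establish successful parent randomization effectiveness". The variables it names for this are drinking before treatment, consequences and demographics. The entry rule comes next: "Any student variables that are associated with treatment assignment, in spite of parent randomization, will be included as covariates". The SAP names no test, significance level or list of variables, and does not say whether a flagged variable enters as a main effect or also by time.

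The Protocol's Measures Appendix already collects items that could plausibly predict drinking, for example the self-rating that begins "Which best describes your alcohol use", age at first drink, and frequency of contact with each parent.

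**The concern.** Under valid randomization, every association between a baseline variable and arm is a chance event. A significance test of it answers a question whose answer is known, and it cannot show that randomization worked.

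As a selection rule it looks at the wrong property. Adjustment helps in proportion to a covariate's relation to the outcome. Under this rule a strong predictor of drinking with a moderate, unflagged imbalance stays out, while an irrelevant variable that happens to differ goes in. Because no cut-off is stated, what counts as associated is also left to the analyst, after arm and baseline data have been joined.

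Two side effects follow. A flagged baseline drinking measure would become a covariate while also being the time-0 outcome, which the SAP does not address. And since "The randomizer will be set up in Qualtrics to balance assignment to an app condition by students' birth sex", birth sex will almost never be flagged, whatever its relation to drinking.

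**Working it through.** **Inputs.** From the SAP, Power: 300 per arm, 20% attrition (300 × 0.80 = 240 per arm), target d = 0.20. Assumed, because the documents give none: a two-sided 5% cut-off for the baseline tests, 8 to 15 independent tests, and a correlation r between covariate and the quantity analysed. The plan gives no figure for this rule, so there is none to reproduce.

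**1. Spurious entry.** P(at least one) = 1 − 0.95^k.
- k = 8: 34%
- k = 10: 40%
- k = 12: 46%
- k = 15: 54%

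At a 10% cut-off, k = 8 to 15 gives 57% to 79%. Correlated items lower these figures.

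**2. Imbalance that escapes.** The largest unflagged difference is 1.96 × √(2/n). At 300 per arm it is 1.96 × √(2/300) = 0.16 SD; at 240 it is 0.18 SD. At 300 per arm, an unflagged difference of that size shifts an unadjusted follow-up comparison by 0.16 × r: 0.05 SD for r = 0.3 and 0.11 SD for r = 0.7. That is 24% to 56% of the d = 0.20 target.

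**3. Type I error.** Write the unadjusted statistic as r·z_x + √(1 − r²)·e, where z_x is the covariate's imbalance statistic. Adjust only if |z_x| > 1.96.

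| r | Overall, under the rule | Given 1.5 < abs(z_x) < 1.96 (not flagged) |
|---|---|---|
| 0.3 | 4.8% | about 7% |
| 0.4 | 4.6% | about 8% |
| 0.5 | 4.3% | about 10% |

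The conditioning event has probability 2 × [Φ(1.96) − Φ(1.5)] = 8.4%.

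**4. Power.** Simulation of a single follow-up comparison: 240 per arm, d = 0.20, two-sided 5%, 8,000 runs.

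| r | Never adjust | Test, then adjust | Always adjust |
|---|---|---|---|
| 0.3 | 0.60 | 0.60 | 0.64 |
| 0.5 | 0.59 | 0.60 | 0.72 |
| 0.7 | 0.60 | 0.62 | 0.87 |

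The test-based rule recovers almost none of the available gain.

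**5. Which estimates are touched.** In the SAP's Gaussian random-intercept model with complete data, each slope effect is the between-arm difference in mean within-person change. A time-fixed covariate entered as a main effect cancels from it. Simulation with assumed values (300 per arm, covariate coefficient 0.5, outcome variance 1, within-person correlation 0.5, 60 runs per setting) gave:
- Complete data: the last-visit slope effect changed by about 1e-14, and its SE was 0.0816 with and without the covariate.
- 20% missing at the last visit: the slope effect moved by at most 0.02 SD; SE 0.0876 without and 0.0872 with the covariate.
- Arm difference at the last visit: adjustment moved it with an SD of about 0.043, in line with 0.5 × √(2/300) = 0.041. For a single visit with r = 0.5, the SE falls by 1 − √(1 − 0.25) = 13%.
- Covariate-by-time entry (a separate 40 runs, 240 per arm, assumed coefficients): the slope itself moved by up to 0.07 SD, about a third of the d = 0.20 target.

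Steps 2 to 4 therefore describe the comparisons at each time point. They describe the slopes only if r is the correlation with change and the covariate enters by time.

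**The case against.** The strongest reply is that the SAP's main effect is the treatment-by-time slope, which already removes imbalance in the outcome's own baseline, and that a covariate entered in the ordinary way leaves that slope and its SE alone. This stands for the Gaussian model with complete data, and nearly so with 20% missing. A reader might infer that the effect estimates for all three outcomes hinge on which variables are flagged. The documents do not support that: it would need by-time entry, which the SAP neither states nor rules out. The invariance was not checked for the Poisson form the SAP also considers.

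A reader might also infer that the rule breaks error control. It does not. Overall type I error is slightly below 5%; the 7% to 10% figures belong to a slice of about 8% of trials. They show conditional bias, not an inflated test.

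Thirdly, one could count every appendix item and assume 15 to 25 independent tests, giving 54% to 72%. The SAP names alcohol use, consequences and demographics rather than the whole questionnaire, the drinking items overlap, and birth sex is balanced by design. The lower range is the defensible one.

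What remains is that arm association is the only way in, that the time-point comparisons are planned, and that even the consequence of a flag is undefined.

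**Conclusion.** The point holds as a flaw in a stated rule, not as a threat to the trial's overall type I error. The rule selects covariates by chance imbalance, cannot confirm randomization, and leaves the model unknown until arm is joined to baseline data. The harm is lost precision and conditional bias in the between-arm comparisons at each time point. For the slopes it is nil under main-effect entry with complete data, small with missing data, and material only under by-time entry. The sizes rest on an assumed 5% cut-off, 8 to 15 independent tests, assumed correlations of 0.3 to 0.7, and a Gaussian model. The direction does not depend on these values, provided the covariate is related to the outcome. The change should be made before arm and baseline data are joined.

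**What to change.** Delete the rule that variables associated with assignment are added, and replace it as follows.

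- Fix now a short list of covariates measured at the student baseline, which precedes the parents' randomization, chosen for expected relation to first-year drinking. Candidates already collected are self-described drinker category, age at first drink, and frequency of contact with mother and father. Leave out current living arrangement: the baseline survey is in July, before matriculation, so it would not capture where students live at college, and a follow-up answer would be post-randomization.
- State for each whether it enters as a main effect or also by time. By-time entry is needed for any worthwhile precision gain on the slopes; main-effect entry serves the comparisons at each time point.
- Use the list in every primary model, whatever the observed balance.
- Report baseline characteristics by arm descriptively, without significance tests.
- Show any adjustment prompted by an observed imbalance only as a labelled sensitivity analysis.

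The cost is SAP wording and a few degrees of freedom; no new data are needed. The one real concession is that a chance imbalance in an unlisted variable is then handled only in the sensitivity analysis.

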2. SUBJECT RECRUITMENT

How will subjects be selected? What is the sex and age range of the subjects? Approximately how many subjects will be studied?

How will subjects be contacted? Who will make initial contact with subjects? Specifically, what will subjects be told in initial contact?

If subjects will be screened, describe criteria and procedures.

This study seeks to evaluate both feasibility and efficacy of the FITSTART+ app-based intervention for parents. The goal is to assess efficacy of the intervention version of the FITSTART+ app on student alcohol outcomes, relative to an active control version of the app. Participants in the clinical trial will ultimately be 400 to 600 LMU students who have a parent randomized to use either the intervention or control version of the app. The Registrar will provide student and parent contact information for the incoming freshman class (approx. 1600 students and 3000 parents). Incoming traditional, non-international first-year students (i.e., first-time college students aged 17–20 years) registered to attend LMU during the Fall semester and who have at least one parent/guardian email on file with the admissions office will be emailed an invitation to participate in a three-part web-based survey assessing experiences during their first year of college. Invitations to complete the baseline survey will be sent in July 2021 (T1) via the admissions office who will verify each student's age, year in school, and whether they have a parent/guardian email on file. The baseline survey and each follow-up survey will be open for

approximately 3 weeks. Student participants will receive a \$25 electronic gift card for completing each study survey and an additional \$10 bonus if they complete all three surveys.

To participate in the study, students must:

- 1) Be a first-year college student 17–20 years of age.
- 2) Have a parent/guardian email on file with the admissions office.
- 3) Be a domestic (i.e., non-international) student.
- 4) Consent to participate (with parental consent for minors under age 18).

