3. PROCEDURES

Summarize fully all procedures to be conducted with human subjects.

This intervention study tests the feasibility of the FITSTART+ program and evaluates the effects of the parent-program on student drinking. That is, the program will be delivered to parents exactly as it might be delivered in the real world, out of the study context (no incentives, knowledge of condition assignment, or awareness of associated student survey study). Simultaneously, alcohol use outcomes will be assessed among the first-year students of participating parents with students incentivized to complete 3 surveys spanning their first year. Recruitment will begin in July 2021 prior to matriculation and will be identical to the IRB approved recruitment procedure in our successful previous R21 FITSTART project (LMU IRB 2014 SP 45). In early summer, the Registrar will provide the research team with new student and parent contact information.

Emails sent by the university's admissions office will only invite students who meet our eligibility criteria to participate in a 3-part longitudinal survey study about their transition into college life. These invitations will mention that they will receive \$25 for each 15-minute survey and an additional \$10 bonus if they complete all three (for a total of \$85). This email will contain a link for interested students to complete the IRB-approved informed consent form. When consenting, students indicate whether they are 18 years of age or older, or under 18. Students 18 or older will provide consent while those under the age of 18 who wish to participate will provide assent and then will be asked for their parent's email address and their parents will be sent a consent form (Consent Appendix). As part of the consent form, students will also agree to the potential linking of their data with data provided by their parent(s) who may also be participating in a separate study. The form will specify that their survey responses will NOT be shared with their parents under any circumstances and their participation in the study will be confidential. If students agree to the potential parent-data linkage, they will immediately be redirected (triggered automatically by Qualtrics) to begin the baseline survey. Incoming first-year student recruitment will continue until 700 students have completed the baseline survey.

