All parents of students who complete the baseline survey will be invited via email to take part in the FITSTART+ program. To sign up, parents will need to click a link in the email to visit the FITSTART+ landing page which will include a general description of the application (no information about alcohol), a description of the parenting experts featured in the application, and a parent verification form. The verification form, which will be a Qualtrics survey embedded in the landing page, will serve two important purposes: it will (1) match parents to their students in the dataset; and (2) randomize parents to the treatment or control version of the app. The randomizer will be set up in Qualtrics to balance assignment to an app condition by students' birth sex. At the end of the verification form, parents will receive a web URL linking to the sign-up page for the application to which they were randomized. Parents who click the link will be prompted to create their user account. In order to not artificially bias parents' app use, parents will be unaware that there is more than one version of the app, they will not be incentivized to use the app, and they will not be told that their child is participating in a survey study.

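### Does the unquantified claim of excellent power at 300 per arm require a change to the plan?

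*SAP*

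**What the plan says.** The Power paragraph of the SAP states that the trial "aimed for sufficient statistical power to detect small effects on our primary student drinking outcomes". The calculation was done in Optimal Design for a longitudinal multilevel model with two conditions and person-level randomisation. Curves were drawn with 20% attrition at d=.20 and d=.40, and the result is given in words: "A sample size of 300 per arm was found to yield excellent power for detecting both effect sizes".

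The Protocol (section 2, Subject Recruitment) gives the trial size as a range: "Participants in the clinical trial will ultimately be 400 to 600 LMU students who have a parent randomized". Section 3 (Procedures) adds that "Incoming first-year student recruitment will continue until 700 students have completed the baseline survey", and says of parents that "they will not be incentivized to use the app".

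The SAP's model has a random intercept, two follow-up dummies and their interactions with treatment, so that "slope differences will represent changes over time". Pairwise comparisons "were conducted to examine mean differences between conditions at each time point". Under Additional Model Considerations the error distribution is left open: "Alternative models could also specify a Poisson or Gaussian distribution for the Level 1 errors".

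**The concern.** A power statement normally lets a reader repeat the calculation. This one does not, because its result is an adjective and several inputs are absent. For a change-from-baseline contrast, power depends strongly on how closely a student's repeated reports correlate, and nothing in either document fixes that correlation.

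The statement also speaks only to 600 students, the ceiling of the Protocol's range. With recruitment closing at 700 baseline completers, reaching 600 needs a parent to sign up for 600/700 = 86% of them, and reaching 400 needs 400/700 = 57%. The Procedures section has the programme delivered to parents without incentives, so a total below 600 is quite possible.

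If r is moderate, the aim of detecting small effects might be missed, and a null result could be taken as stronger evidence than it is.

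**Working it through.** **The plan's own figure.** There is no number to reproduce. The wording can only be tested against assumed inputs.

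**Inputs from the documents.** d=.20 and .40; 300 per arm; 20% attrition (SAP, Power). Total of 400 to 600, so 200 to 300 per arm if allocation is equal (Protocol, section 2). After attrition, n = 0.8 × 300 = 240 or 0.8 × 200 = 160 per arm.

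**Assumed, because not stated.** Two-sided .05; d in SD units of the outcome at one time point; equal correlation r between waves, as a Gaussian random-intercept model implies; analysis of completers.

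**Formulas.** Power = Φ(δ − 1.96), with δ = (d/s)·√(n/2).

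- One follow-up against baseline: s = √(2(1 − r)).
- Mean of both follow-ups against baseline: s = √(1.5(1 − r)).

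Example: d=.20, r=.5, n=240, one contrast. s = 1, δ = .20 × √120 = 2.19, power = Φ(0.23) = 59%.

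**Power for d=.20**

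| Contrast | Students | r=.3 | r=.5 | r=.7 | r=.8 |
|---|---|---|---|---|---|
| One follow-up | 600 | 46% | 59% | 81% | 93% |
| One follow-up | 400 | 33% | 43% | 64% | 81% |
| Mean of two | 600 | 57% | 72% | 90% | 98% |
| Mean of two | 400 | 42% | 54% | 76% | 90% |

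**Correlation needed.** Solving for r with one contrast gives r = 1 − (n/4)·(d/(1.96 + z))², where z is .84 for 80% power.

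- n=240: 1 − 60 × (.20/2.80)² = .69.
- n=160: 1 − 40 × (.20/2.80)² = .80.
- For 90% power: .77 and .85.
- Mean of two follow-ups (n/3 in place of n/4): .59 and .73 for 80%; .70 and .80 for 90%.

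**Sensitivity of the 80% thresholds at 600 and 400 students (one contrast unless noted)**

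- 15% attrition, matching the SAP's expectation of keeping over 85%: .68 and .78.
- Random-intercept model with incomplete cases kept, month-6 contrast: .68 and .79.
- Baseline-adjusted comparison at one follow-up (not the SAP's model): .62 and .77.
- Bonferroni over three outcomes (not in the SAP): .77 and .85.
- If 600 is the number analysed, n=300 and the threshold is .62; the mean of two follow-ups at r=.5 then reaches 81%.
- If d is in SD units of change, or a single time point is compared without using baseline, r drops out and power for d=.20 is 59% at 600 and 43% at 400.

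**Power for d=.40, one contrast**

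| Students | r=0 | r=.3 | r=.5 |
|---|---|---|---|
| 600 | 87% | 96% | 99% |
| 400 | 72% | 86% | 95% |

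**The case for a change.** The strongest case for a change is that one sentence carries the whole power argument and cannot be checked. Under plausible readings its claim for d=.20 fails. At r=.5 a single contrast has 59% power at 600 students, and 43% at 400. The favourable variants still need r near .6 at 600 and above .7 at 400. The repair would be cheap, since the sponsor has already run the calculation.

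Much of this stands. The omissions are real, nothing elsewhere in the SAP or Protocol supplies the inputs, and no power is given below 600.

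What does not stand is the step from an unstated input to inadequate power. Every percentage above rests on an alpha, standardiser, correlation and contrast that the reader has to choose. The documents do not show that r of .6 to .7 or more is unrealistic for repeated self-reports by the same students. The 20% attrition used is also more cautious than the 13% the SAP reports from its earlier study.

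The number of tested contrasts, the three outcomes and the parent sign-up rate are separate questions. They concern multiplicity and feasibility. The power sentence cannot settle them.

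**Conclusion.** No change to the plan is needed. The Power paragraph is incompletely reported, but its statement about 300 per arm is not shown to be false. It is credible for d=.40: 96 to 99% at 600 students, and still 86 to 95% at 400, for r from .3 to .5. For d=.20 it holds if r is high enough: 80% power needs about .69 at 600 and .80 at 400 for one contrast, or about .59 and .73 for the mean of both follow-ups. These figures assume two-sided .05, d in outcome-SD units, 20% loss, completers and Gaussian outcomes. They are approximate if a Poisson model is chosen.

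Stating the inputs would make the paragraph easier to audit. It would not alter who is enrolled, what is measured, which model is fitted or what is estimated. Once the data are in, the confidence intervals show the precision achieved, whatever was assumed at the design stage. The practical caution is for interpretation: with totals near 400, a non-significant result should not be read as ruling out a small effect.
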